6.4.5. Overall Study Period

Overall Study Period is defined as the time from the date of first study treatment to the Common Study End Date (CSED).

6.5. Baseline Definition

Unless otherwise specified, baseline is defined as the last non-missing measurement taken prior to first dose of study treatment (including unscheduled assessments). In the case where the last non-missing measurement and the first dose date coincide, that measurement will be considered pre-baseline, but Adverse Events (AEs) and medications commencing on the first dose date will be considered post-baseline.

6.6. Derived and Transformed Data

6.6.1. Baseline Age

Subjects' age in years will be calculated based on date of informed consent date using the following formula:

Age (year) = FLOOR((date of informed consent - date of birth)/365.25)

where FLOOR() function returns the integer part of the result. If any component of the date of birth is unknown, the subject's baseline age will be taken directly from the eCRF.

6.6.2. Study Day

If the date of interest (i.e., event date, assessment date, etc.) occurs on or after the date of first dose of study treatment then study day will be calculated as (date of interest – date of first dose) + 1. If the date of interest occurs prior to the date of first dose of study treatment then study day will be calculated as (date of interest – date of first dose). There is no study day 0.

6.6.3. Change from Baseline

Change from baseline is calculated as (post-baseline result – baseline result).

Percent change from baseline is calculated as ((change from baseline/baseline result) * 100).

If either the baseline or the post-baseline result is missing, the change from baseline and/or percentage change from baseline is set to missing as well.

6.6.4. Visit Windows

No visit windowing will be applied to this study. For by-visit summaries, data recorded at the nominal visit will be presented. If multiple assessments occur within a visit, the result closest to the protocol defined visit will be used for the by-visit summaries.

Unscheduled measurements will not be included in by-visit summaries, but would be included in time to event analyses.

6.7. Handling of Missing Data

Every effort will be made to minimize missing data throughout the trial, from the design phase through follow-up.

Right censoring will apply for any time to event analyses.

For select continuous measures, missing data will be addressed using Mixed-Effect Model Repeated Measure (MMRM) methods.

6.7.1. Missing Endpoint Dates

For time to event analyses, only observed events will be used and censoring will be assumed to be non-informative for the main analyses. Partially missing endpoint event dates will be imputed using the start date and end date of the Overall Study Period after due diligence to obtain accurate information has failed. A conservative imputation approach will be implemented such that more events will be included in the analyses. If the known components of the endpoint date indicate the event occurred in the same month as the start of the Overall Study period, the event day will be imputed using the Overall Study period start day. If the known components show the event occurred in the same year as the start of the Overall Study period, the event month and day will be imputed using the Overall Study period start day and month. Similarly, if the known components of the endpoint date indicate the event occurred in the same month as the end of the Overall Study period, the event day will be imputed using the Overall Study period end day. If the known components show the event occurred in the same year as the end of the Overall Study

period, the event month and day will be imputed using the Overall Study period end day and month. For missing date components falling outside the assumptions outlined previously, a conservative imputation approach will be implemented in regards to time to event. If only the year is known, the event day and month will be assigned to January 1st. If the month and year are known, the event day will be assigned to the first day of the month.

6.7.2. Missing Start and Stop Dates for Prior and Concomitant Medication

Imputation of partially missing dates would follow the conservative imputation approach as defined in section 6.7.1. When needed for summary tables of analysis, imputation for missing prior and concomitant medication use would be done using the rules below.

Start Date	Stop Date	Prior	Concomitant		
Missing	Missing	Yes	Yes		
Missing	Before First Dose	Yes	No		
Before First Dose	Missing	Yes	Yes		
Missing	After First Dose	Yes	Yes		
After First Dose	Missing	No	Yes		

6.7.3. Missing Start and Stop Dates for Adverse Events

Completely missing or partially missing AE onset dates will be imputed as follows after due diligence to obtain accurate AE information has failed. If the event date is completely missing and could have occurred after the start of therapy, the date will be set to the start date of therapy. Partially missing event dates will be imputed using the start date and end date of the Overall Study Period. A conservative imputation approach will be implemented such that more events will be considered treatment emergent.

7. STUDY POPULATION

7.1. Subjects Disposition

The number of patients in each population will be presented overall and by region and site for all randomized subjects.

Subject disposition and withdrawals will be presented by treatment group and overall. This summary includes total number of subjects completing the study and total number of subjects discontinuing from the study and reasons for discontinuation. Patients who withdrew from the study will be presented in a listing.

Descriptive statistics of the number of days in trial will also be summarized. Number of days on trial will be calculated as: date of end of participation (from EOS form) – date of randomization +1.

Additional replicate tables may also be generated presenting the same accounting and disposition data for important sub-sets of the study, including by region or country. Graphical summaries including Kaplan-Meier plots of the dropout patterns will also be provided so that it can be clearly seen if there is a differential dropout pattern between the treatment groups. The number and percent of subjects who completed follow-up will be summarized by treatment group. A subject will be counted as 'completed follow-up' if the subject is known to be dead or has completed an assessment visit at the end of the study. Otherwise, a subject will be counted as 'incomplete follow-up'.

7.2. Screen Failures

The demographic profile of subjects who terminate the trial as screen failures will be summarized and presented in a listing or a submitted dataset.

7.3. Protocol Deviations

Deviations from the protocol which, based on clinical input, may have an impact on the efficacy analyses will be presented. These are related to study inclusion or exclusion criteria, conduct of the trial, subject management or subject assessment. The number of patients with ITT population and protocol deviation type will be presented. Protocol deviations identified by type will also be presented in a listing.

Prior to database lock and unblinding, subjects and the protocol deviation type will be given to bios to present the reason.

7.4. Demographic and Baseline Characteristics

Demographic data and other baseline characteristics will be presented for the ITT population. Statistical testing will be carried out for baseline characteristics for descriptive purposes only. Chi-square tests will be performed on categorical results and Wilcoxon rank-sum tests will be performed on continuous and ordinal results.

The following demographic and other baseline characteristics will be reported for this study:

Demographics

- Age (years)
- Age categorized (<55, >=55)
- Sex
- Race
- Ethnicity
- Region

Baseline Characteristics

- Height (cm)
- Weight (kg)
- BMI (kg/m²)
 - \circ BMI (kg/m²) = weight (kg)/height (m)²
- BMI categorized (<30, $>=30 \text{ kg/m}^2$)
- Waist circumference (cm)

Cardiovascular Diseases and Risk factors

- Smoking Status (Current Smoker, Past Smoker, Never Smoked)
- Statin Use (defined hierarchically by the following categories: 1) moderate/high intensity statin, 2) Statin intolerance, 3) LDL-C < 70 mg/dL (1.81 mmol/L))
- Congestive Heart Failure (Yes/No)
- Prior MI (Yes/No)
- Prior Coronary Revascularization (Yes/No)
- Peripheral Artery Disease (Yes/No)
- HbA_{1C} (% and mmol/mol)
- HbA_{1C} categorized ($\leq 8.5\%$; >8.5%)
- Systolic Blood Pressure (mmHg)
- Diastolic Blood Pressure (mmHg)
- Pulse (beats/min)
- HDL-C (mg/dL)
- LDL-C (mg/dL)
- Apo B

- Remnant-C (mg/dL)
- Apo C-III (mg/dL)
- Fasting TG (mg/dL)
- Non-fasting TG (mg/dL)
- Diabetes duration (years)
- Hypertension (Yes/No)
- eGFR
- eGFR categorized (\leq 53 mL/min/1.73m²; >53 mL/min/1.73m²)

7.5. Listing of Subject Inclusion and Exclusion Criteria

Although compliance with subject selection criteria is not routinely summarized in table format, these data will be listed on an individual subject basis as needed for all randomized subjects.

7.6. Medical History and Medical Conditions Present at Entry

Past medical history and medical conditions present at entry will be described separately for the ITT population. A medical condition will be considered present at entry if the stop date is unknown or the condition is reported as ongoing at the time the medical history was obtained.

Conditions will be coded according to MedDRA dictionaries where information is available and summarized by System Organ Class (SOC) and Preferred Term (PT).

7.7. Prior Medication History

Prior medication history will be described separately for the ITT population. A medication will be considered prior medication history if the medication start and stop dates are prior to first dose of study treatment. Missing dates will be imputed according to the method outlined in section 6.7.2.

All medications will be coded using the WHO dictionary and summarized by preferred term and drug classes (level 3 – therapeutic class). Anatomic-Therapeutic Class (ATC) coding will be used to define diagnosis-related drugs.

7.7.1. Non-Diagnosis Related Prior Medication History

This supportive listing, limited to non-diagnosis related medications, will include the unique data associated with medication start and stop dates, dose, frequency of administration, route of administration, trade name, generic name, and why it was prescribed. Non-Diagnosis related medications will be identified as drugs used in diabetes and not related as in section 7.7.2 Diagnosis related prior medication history.

Kowa Research Institute, Inc. Statistical Analysis Plan – Protocol K-877-302 (PROMINENT)

February 03, 2021

7.7.2. Diagnosis Related Prior Medication History

Similar listings as described in Section 7.7.1 will be provided for diagnosis related prior medications. Diagnosis related medications will be identified by ATC coding level 2 equal to "DRUGS USED IN DIABETES".

8. EFFICACY

8.1. General Considerations

The following will be applied to all efficacy analyses where applicable.

The ITT population will be used in the analysis of efficacy endpoints. Endpoints will be summarized by treatment group unless otherwise stated. Results will be presented by region and center where appropriate. Extreme results by region or center will be noted.

The summary statistics for the efficacy endpoints and their individual components will be provided. These statistics include the number of first events (i.e. the number of subjects with the event), the total exposure to first event or censoring time, the annualized event rate, and the Kaplan Meier estimates, when applicable. The annualized event rate will be calculated as the number of subject with events divided by the total time at risk (years) to the subjects' first event or censoring time. The hazard ratio of the exposure group versus placebo with 95% CIs will be provided using the Cox proportional hazards model including treatment. The model will be stratified by the three stratification variables, sex, prior history of CVD, and baseline statin use, under the assumption of differing baseline hazards.

8.2. Statement of the Null and Alternate Hypotheses

The primary statistical null and alternative hypotheses are:

H_O: The hazard rate of first occurrence of any component of the clinical composite endpoint of nonfatal myocardial infarction, nonfatal ischemic stroke, coronary revascularization, or cardiovascular death in the K-877 treatment group is equal to the hazard rate in the placebo group

H₁: The hazard rate of first occurrence of any component of the clinical composite endpoint of nonfatal myocardial infarction, nonfatal ischemic stroke, coronary revascularization, or cardiovascular death in the K-877 treatment group is not equal to the hazard rate in the placebo group

8.3. Subgroup Analyses

Subgroup analyses will be conducted for the primary endpoint and each individual component as well as other endpoints as needed. Where applicable, each subgroup will be analyzed using a Cox proportional hazard model including treatment and the two stratification variables: sex and prior history of CVD. Due to the low level of statin intolerance at baseline, primary subgroup analyses will not stratify on statin use at baseline. The descriptive summaries and the two sided 95% CIs for the hazard ratio will be provided. Likelihood tests for treatment by subgroup interaction comparing models with and without interaction terms between treatment and categories will also be assessed. While a formal test for heterogeneity of treatment effect by country or center has not been prespecified, center level deviations will be monitored across multiple operational quality measures such as rate of discontinuation of study drug to ensure there are no systematic differences introduced during the study.

The subgroups may be based on characteristics including but not limited to the list below.

Variable	Categories			
Baseline Subgroups				
Sex	Men, Women			
Established Cardiovascular Disease	Yes, No			
Statin Use	Defined as those who are taking no statin at baseline or are statin intolerant compared to all others.			
Region	Africa,			
	Asia (comprising Japan, Israel and India),			
	Eastern Europe,			
	Latin America,			
	US/Canada,			
	Western Europe			
Age	<65,			
	>=65			
BMI (kg/m²)	<30,			
	30-34,			
	>=35			
Race	Asian,			
	Black or African American,			
	White,			
	Other (including, Other, Multiracial and Not Reported)			
Ethnicity	Hispanic or Latino,			
	Not Hispanic or Latino,			
	Unknown/Not Reported			
Duration of Diabetes	<10 years,			

	>=10 years			
Hypertension	Yes, No			
HDL	Above/below median at baseline (screening value)			
LDL	Above/below median at baseline (screening value)			
Fasting TG	Above/below median at baseline (screening value)			
Non-Fasting TG	Above/below median at baseline (randomization value)			
Non-HDL Cholesterol	Above/below median at baseline (screening value)			
АроВ	Above/below median at baseline (screening value)			
Non-fasting Remnant Cholesterol	Above/below median at baseline (randomization visit)			
HbA1c	Above/below median at baseline (screening value)			
hsCRP	Above/below median at baseline (screening value)			
CYP3A4 or CYP2C8 Inhibitor Use	Yes, No			
Ezetimibe Use	Yes, No			
PPAR-α rs6008845 genotype	TT variant, TC variant, CC variant			
On-Treatment Subgroups				
On-Treatment Fasting TG	Above/below the median of the on-treatment values in the pemafibrate group at a fasting 4 Month visit.			

On-Treatment Non-Fasting TG	Above/below the median of the on-treatment values in the pemafibrate group at a non-fasting 6 Month visit.			
On-Treatment Non-HDL Cholesterol	Above/below the median of the on-treatment values in the pemafibrate group at 4 Month visit.			
On-Treatment ApoB	Above/below the median of the on-treatment values in the pemafibrate group at 4 Month visit.			
On-Treatment Non-Fasting Remnant Cholesterol	Above/below the median of the on-treatment values in the pemafibrate group at 6 Month visit.			
On-Treatment hsCRP	Above/below the median of the on-treatment values in the pemafibrate group at 4 Month visit.			

Subgroup analyses may also be added to safety presentations as needed.

Forest plots will be generated for the subgroup analyses.

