A thorough QT/QTc (TQT) study was conducted, which demonstrated that neither clinical (0.4 mg) nor supratherapeutic (1.6 mg) single doses of pemafibrate caused prolongation of the corrected QT (QTc) interval.

The efficacy and safety of pemafibrate was evaluated in 6 clinical studies of up to 12 weeks duration at daily doses ranging from 0.05-0.4 mg taken once daily or divided twice daily in participants with dyslipidemia and: (1) HTG; (2) HTG with low HDL-C; (3) HTG with elevated non-HDL-C. Pemafibrate was used as monotherapy and in combination with statins in both diabetic and non-diabetic participants. Major efficacy and safety findings are summarized below.⁶⁰

Efficacy

Treatment with pemafibrate produced statistically significant and clinically relevant reductions in fasting plasma TGs, and also reduced postprandial HTG. Other effects on lipids and lipoproteins, included reductions in non-HDL-C, total cholesterol (TC), very low-density lipoprotein cholesterol (VLDL-C), remnant-like lipoprotein particle cholesterol (RLP-C), ApoB, ApoB48, ApoC2, ApoC3, and increases in ApoA1, ApoA2, and HDL-C were also observed.

Increases in LDL-C were observed in some studies; however, the absence of corresponding increases in ApoB suggests that this change is not associated with an increase in LDL particles.

Safety

The adverse events (AEs) in the pemafibrate group tended to occur at rates similar to those in the placebo or active comparator (fenofibrate at 100 or 200 mg/day) groups. No AE pattern indicative of organ system toxicity or pathophysiology was observed. The occurrence of AEs related to transaminase elevation (eg, liver function test abnormal, alanine aminotransferase

[ALT] increased, or aspartate aminotransferase [AST] increased) in the pemafibrate group occurred at frequencies higher than those in the placebo group, but lower than those in the fenofibrate group. In general, transaminase and γ -glutamyl transpeptidase (GGT) levels decreased from baseline and increases in AST or ALT \geq 5 × upper limit of normal (ULN) were infrequent. Mean creatinine levels increased with pemafibrate, but at a lower magnitude and incidence than those with fenofibrate; these increases were not clinically significant, and very few AEs were reported. Statistically significant decreases in mean fibrinogen levels were noted in multiple studies; however, these changes did not occur in the setting of AEs, so the clinical relevance of this decrease is unknown.

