14.6. Subgroup Analyses

Additional planned exploratory analyses include evaluation of whether treatment effects vary across categories of baseline covariates. Key prespecified subgroup analyses will examine treatment effect by sex, prior CVD, and baseline statin use. Other subgroups of interest include region, age, race, baseline lipid levels, and other baseline biomarker levels. Within each subgroup, we will use proportional hazards models to estimate the relative rate of the primary endpoint associated with active treatment versus placebo. Both crude analyses and models including limited baseline covariates will be fitted. To test for the significance of modification of treatment effects by a baseline characteristic, we will include interaction terms between this characteristic and treatment in the proportional hazards model, with statistical significance determined by a likelihood ratio test comparing models with and without the interaction terms

Confidential K-877-302 Study Protocol

Version 3 dated 18-Mar-2020

between treatment and the categories of a specific covariate. While a formal test for heterogeneity of treatment effect by country or center has not been prespecified, center level deviations will be monitored across multiple operational quality measures such as rate of discontinuation of study drug to ensure there are no systematic differences introduced during the study.

Subgroup analyses will be conducted regardless of whether or not the overall analyses of treatment effects are significant. Our approach to interpretation of subgroup analyses has always been very cautious and recognizes that, even in large studies, it is not likely to be possible to identify reliably subgroups of participants in whom treatment is especially effective or ineffective. In the absence of prior evidence for real heterogeneity, the overall study result may provide the best evidence for the presence of a benefit in a subgroup. Our approach thus corresponds to an informal empirical Bayes procedure in which effects in an outlying subgroup require interpretation in light of the overall treatment effect.

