8.4. Analysis of the Primary Efficacy Endpoint

8.4.1. Primary Efficacy Analysis

The primary endpoint of the trial is the time from randomization to the first occurrence of any component of the clinical composite endpoint of nonfatal myocardial infarction, nonfatal ischemic stroke, cardiovascular death, and coronary revascularization.

Patients who do not have an event will be censored at withdrawal of consent, end of study, or death. The censor date will be the date of withdrawal of consent for follow-up, CSED or the subject's last assessment, or death, whichever comes first. The time to event/censoring in days will be derived as (Date of First Occurrence of Event/Censoring – Date of First Dose) +1. The primary analysis of the trial will use a likelihood ratio test based on a proportional hazards model stratified on sex, prior history of CVD, and statin use at baseline to test the null hypothesis of no association between assignment to active K-877 and the rate of the primary endpoint. All analyses will classify patients according to their randomized treatment assignment, i.e. according to the intention to treat principle, and will base evaluation of statistical significance on a two-sided test with level 0.05. The estimated relative hazard in the K-877 group compared to the placebo group with an accompanying 95% confidence interval will quantify the treatment effect. If this relative hazard is less than 1, then 100*(1-estimated relative hazard) will be defined as the percent reduction in hazard associated with K-877 treatment. Rates of occurrence of the primary endpoint will be defined as the total number of subjects who have this event in a treatment group per 100 person-years of follow-up. Estimates of the probability of the primary

```
Kowa Research Institute, Inc.
Statistical Analysis Plan – Protocol K-877-302 (PROMINENT)
```

endpoint by time after randomization within treatment groups will be based on the method of Kaplan and Meier.

Analysis will be implemented using the SAS® procedure PHREG as follows:

```
PROC PHREG DATA = ...;

CLASS TREATMENT (ref='2');

MODEL AVAL*CNSR(1) = TREATMENT;

STRATA SEX CVD STATIN;

HAZARDRATIO TREATMENT / ALPHA=0.05;

RUN;

where AVAL = time to event

TREATMENT = Randomized treatment group (pemafibrate and placebo)

CNSR = Censoring variable - 0 = Event, 1 = Censored

SEX = sex

CVD = prior history of CVD

STATIN = statin use at baseline
```

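### SAP 8.3 plans pemafibrate-versus-placebo hazard ratios within six subgroups defined by Month 4 or Month 6 biomarker levels that the drug itself changes, so those ratios are not randomized comparisons

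*SAP*

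**What the plan says.** SAP 8.3 has one subgroup table and one method. Where applicable, "each subgroup will be analyzed using a Cox proportional hazard model including treatment and the two stratification variables", namely sex and prior CVD, with a 95% CI for the HR. The section adds "Likelihood tests for treatment by subgroup interaction comparing models with and without interaction terms", and then "Forest plots will be generated for the subgroup analyses".

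The table has two blocks, baseline and on-treatment. The on-treatment block has six rows: fasting TG, non-HDL-C, ApoB and hsCRP at Month 4, and non-fasting TG and non-fasting remnant cholesterol at Month 6. Each is cut at the pemafibrate-arm median, for example "Above/below the median of the on-treatment values in the pemafibrate group at a fasting 4 Month visit". No separate model, comparator, start of follow-up or caveat is given for this block.

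Protocol 14.6 describes exploratory "evaluation of whether treatment effects vary across categories of baseline covariates" and adds "Our approach to interpretation of subgroup analyses has always been very cautious". Protocol 4.7.2 reports: "Treatment with pemafibrate produced statistically significant and clinically relevant reductions in fasting plasma TGs, and also reduced postprandial HTG". The same paragraph lists reductions in non-HDL-C, remnant-like particle cholesterol and ApoB. For hsCRP, protocol 4.4 makes only a class-level statement about anti-inflammatory activity.

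**The concern.** A baseline subgroup contains comparable people in both arms because membership is fixed before treatment. Here half of the pemafibrate arm falls below the cut by construction, while a smaller share of placebo does whenever the drug lowers the marker. The placebo participants below the cut are those with the lowest natural levels; the pemafibrate participants there include people with higher natural levels brought down by treatment. If the marker predicts events, the two groups in a row differ in underlying risk before any drug effect. Classifying participants by randomized arm does not help, because the row itself is formed after randomization.

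Three things are also left open:

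1. SAP 8.3 does not say how placebo participants are classified.
2. It does not define whether a value taken off drug counts. Under protocol 7.3, once study drug is stopped the investigator decides whether blood is drawn, so having a value at all may depend on staying on drug.
3. It states no later start of follow-up. In SAP 8.4.1, "The time to event/censoring in days will be derived as" days from first dose; if that carries over, events before the Month 4 or Month 6 sample count in the row.

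At stake is a reading of these rows as evidence on whether a lower achieved level helps. That is a central question for a triglyceride trial, and these rows cannot answer it.

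**Working it through.** **Design inputs (documents).** HR 0.834, two-sided alpha 0.05, 90% power, 5,000 per arm, placebo rate 3.5–4.5 per 100 person-years. The event count reproduces: 4(1.960 + 1.282)²/(ln 0.834)² = 1,276, against 1,279 in protocol 14.2; multiplied by 1.019 this is 1,300, against 1,304. Nothing here disputes that figure.

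**Assumed inputs (not in the documents).** Marker log SD 0.40; event HR per SD of the untreated marker 1.1–1.3; lowering 10–35%. Nothing in the documents supports the upper end of that range for ApoB, non-HDL-C or hsCRP. True drug HR is 1.0 and both arms are split at the pemafibrate median.

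**Formulas.** Let s = −ln(1 − lowering)/0.40 and b = ln(HR per SD).

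- Placebo share below the cut = Φ(−s)
- HR below = [Φ(−b)/0.5] / [Φ(−s−b)/Φ(−s)]
- HR above = [Φ(b)/0.5] / [Φ(s+b)/Φ(s)]

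| Lowering | s | Placebo below cut | HR below (1.1; 1.3 per SD) | HR above (1.1; 1.3 per SD) |
|---|---|---|---|---|
| 10% | 0.26 | 40% | 1.02; 1.05 | 1.02; 1.04 |
| 25% | 0.72 | 24% | 1.05; 1.15 | 1.04; 1.10 |
| 35% | 1.08 | 14% | 1.08; 1.24 | 1.05; 1.14 |

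Worked case, 25% lowering and 1.3 per SD: HR below = (0.3965/0.5)/(0.1632/0.236) = 1.15.

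Multiplying by the design HR of 0.834, the rows would show 0.85–0.87 at 10% lowering and 0.87–1.03 at 25–35%. Both halves would look worse than the whole trial.

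**False findings.** Simulation used 1,000 trials per scenario, 3.5 years of follow-up, and 4.13 events per 100 person-years, which is the mean of 4.5 and 4.5 × 0.834. A person-time rate ratio stood in for the Cox model. With true HR 1.0, nominally significant harm (2.5% expected) appeared in 3–8% of trials at 10% lowering. At 25–35% it appeared in 6–31% below the cut and 7–55% above; the top values need 35% lowering and 1.3 per SD together. The interaction test rejected in 5–7%, against 5%. If the marker is not prognostic and adherence is unrelated to risk, the HR is 1.00 with no excess.

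**Non-adherence.** Assume 2–5% off drug at Month 4, an event HR of 1.5–2.0 in those people, and 30% lowering. The HR below the cut is then 0.98–1.00 for a non-prognostic marker, 1.04–1.06 at 1.1 per SD and 1.15–1.19 at 1.3. The 10–17% non-compliance in protocol 14.2 is a trial-level figure and was not used here.

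**The other placebo rule.** If each pemafibrate half were set against all placebo, which the SAP does not state, the HRs would be 2Φ(−b) = 0.79–0.92 in the low half and 2Φ(b) = 1.08–1.21 in the high half: false benefit in one row and false harm in the other.

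**Early events.** 10,000 × [1 − exp(−rate × months/12)] gives 116–149 by Month 4 and 173–222 by Month 6 at the placebo rate in both arms. Applying 0.834 to the pemafibrate arm gives 106–137 and 159–204.

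**The case against.** The rows are exploratory, sit under their own heading and are worded permissively. Protocol 14.6 does not say that only baseline covariates may be used, and it promises caution. The formal tool for heterogeneity is the interaction test, which is barely affected. At 10% lowering the distortion is small. The larger figures rest on assumptions, and they treat the Month 4 or 6 value as the prognostic quantity itself. If the measured value correlates only 0.6 with that quantity (also an assumption), then at 25% lowering and 1.3 per SD the HRs fall from 1.15 and 1.10 to about 1.09 and 1.06, and false harm falls from 21% and 28% to 12% and 15%. One common cut for both arms is the natural reading, so the half-versus-all-placebo case is hypothetical.

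Most of this stands as a limit on size and severity. It does not remove the problem: the permissive wording names no other method and exempts no row. Caution of the kind described in protocol 14.6 guards against chance findings, not a systematic shift in the HRs that the forest plot displays. The mediation assessment in protocol 14.5 is a separate analysis and supplies no method for these rows.

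**Conclusion.** The concern holds. Followed as written, SAP 8.3 puts six post-randomization contrasts beside randomized subgroup comparisons, with nothing to tell the reader they differ. For five of the six markers the documents themselves say the drug lowers the marker or its close equivalent; for hsCRP that is only a class-level expectation, though the row is still defined after randomization. With one common cut and a prognostic marker, both rows move above the true HR, by a few percent under mild assumptions and by up to about a quarter under strong ones. Direction and size depend on the placebo rule and on inputs the documents do not give. The consequence is confined to exploratory interpretation. It should be corrected, but it does not threaten the trial's main conclusion.

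**What to change.** Delete the six on-treatment rows from SAP 8.3, so that treatment HRs, interaction tests and forest plots cover baseline subgroups only. The minimum acceptable change is to take them out of the treatment-HR forest plot and label them non-randomized. Deletion costs SAP wording and the loss of contrasts that cannot be read causally. No replacement is required.

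If achieved level is still to be related to events, add to SAP 8.5:

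> Achieved biomarker level (exploratory, non-randomized association; not the mediation analysis of protocol 14.5). Participants with a Month 4 value (Month 6 for non-fasting markers) and no primary event by that sample; follow-up starts at the sample date. Within each arm, a Cox model relates log achieved level to later primary events, adjusted for log baseline level, baseline risk factors (age, smoking, HbA1c, eGFR, diabetes duration) and tablet-count adherence up to the sample, stratified by sex and prior CVD. No pemafibrate-versus-placebo HR will be shown by achieved level. The report will state that residual confounding by adherence can produce a false lower-is-better gradient.

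This costs modest programming and leaves out the early events counted above. It is not free of bias. I simulated it for a non-prognostic marker (250 runs per scenario, Poisson in place of Cox, assumed Month 4 non-adherence of 2–17% and event HR 1.5–2.0 in non-adherers). A false lower-is-better gradient (2.5% expected) appeared in 4–88% of runs without the adherence term, 1–4% with accurate adherence, and 3–44% when tablet counts missed half of non-adherers (3–9% if non-adherence is only 2–5%). The caveat in the last sentence of the proposed text must therefore stay.
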